9.1. Demographic and Other Baseline Characteristics

Sex, ethnicity, and race of all subjects will be summarized by Dose Group ([Table 12](#)). Ethnicity will be categorized “Hispanic or Latino,” or “Not Hispanic or Latino,” “Unknown,” or “Not Reported.” In accordance with National Institutes of Health (NIH) reporting policies, subjects may self-designate as belonging to more than one race or may refuse to identify a race, the latter reflected in the case report form (CRF) as “No” to each race option. Age at enrollment, height, weight and BMI at Screening will be summarized by Dose Group ([Table 13](#)). Individual subject listings will be presented for all demographic and baseline characteristics ([Listing 6](#)).

9.1.1. Prior and Concurrent Medical Conditions

All current illnesses and past pre-existing medical conditions will be MedDRA coded using MedDRA dictionary version 23.1 or higher. Summaries of subjects’ pre-existing medical conditions by MedDRA system organ class (SOC) will be presented by Dose Group ([Table 14](#)). Individual subject listings will be presented for all medical conditions ([Listing 7](#)).

9.1.2. Prior and Concomitant Medications

All medications will be coded to the Anatomical Therapeutic Classification (ATC) using the current version of the WHO Drug Dictionary. The use of prior and concomitant medications taken during the study will be summarized by ATC 1 and ATC 2 (separately, in [Table 15](#) for prior medications and [Table 16](#) for concomitant medications). Individual subject listings will be presented for all prior medication ([Listing 8](#)) and concomitant medications ([Listing 9](#)).

Regardless of the certainty of the date entered, drugs will be listed and summarized as prior medications when the end date for the medication is before study product administration and listed and summarized as

concomitant medications otherwise. If a medication has no recorded end date it will be considered a concomitant medication.

9.2. Measurements of Treatment Compliance

Date and time of study product administration, along with information on whether the subject was dosed according to protocol will be included in [Listing 10](#). Subject level drug and metabolite concentrations at each timepoint will be included in [Listing 30](#) for plasma and [Listing 31](#) for urine.

9.3. Adverse Events

When calculating the proportions of subjects with AEs within a given MedDRA category, subjects will be counted once for each dosing period within the same MedDRA category, and the event will be reported according to the highest severity recorded throughout the indicated time period (separately for related and unrelated AEs when both severity and relatedness are tabulated). Repeated AEs will be ignored. When calculating the number of AEs that occurred, all AEs will be summarized by Dose Group, including repetitions.

All reported adverse events will be included in the summaries and analyses.

9.3.1. Solicited Events and Symptoms

No solicited events will be collected in this trial.

9.3.2. Unsolicited Adverse Events

An overall summary of unsolicited AEs by Dose Group will be presented in [Table 17](#) including the number of subjects with at least one AE, number of subjects with at least one related AE, and number of subjects with at least one SAE.

All AEs will be presented in [Listing 11](#). A subject listing of non-serious AEs of moderate or greater severity will also be reported ([Table 22](#)).

Denominators for proportions are the number of subjects in the Safety Population in each Dose Group. Placebo subjects who participated in both Cohort 3 and Cohort 6 will contribute to the denominator once per each dosing period for the Placebo Dose Group. Subjects who received VT-1598 and participated in both Cohort 3 and Cohort 6 will contribute to the denominator once per each dosing period for the Any Dose Group. The following summaries for unsolicited AEs will be presented:

- The number of AEs and number and proportion of subjects reporting an AE or SAE that occurred in 5% of all subjects along with the total number of events reported will be presented by Dose Group, SOC, HLTG, and preferred term (PT) ([Table 18](#)).
- The number of AEs and number and proportion of subjects reporting an AE will be presented by Dose Group, SOC, HLTG, and PT. The 95% CI for the proportion of subjects experiencing each SOC/HLTG/PT will also be presented ([Table 19](#)).
- The number and proportion of subjects reporting a related or unrelated AE will be presented by Dose Group, SOC, HLTG, PT, severity, and relationship to study product. ([Table 20](#))

Summaries of unsolicited AEs will be presented graphically in bar charts by Dose Group and SOC. For summaries of proportions of subjects reporting an AE, denominators will be the number of subjects in the Safety Population for each Dose Group. Placebo subjects who participated in both Cohort 3 and Cohort 6 will

contribute to the denominator once per each dosing period. Subjects who received VT-1598 and participated in both Cohort 3 and Cohort 6 will contribute to the denominator once per each dosing period for the Any Dose Group:

- The proportion of subjects reporting a related AE will be presented by the maximum severity reported per SOC ([Figure 3](#)).
- The total number of related AEs reported will be presented by Dose Group and SOC ([Figure 4](#)).

9.4. Deaths, Serious Adverse Events and other Significant Adverse Events

Individual data listings of deaths and other SAEs will be provided ([Table 21](#)). The listing will include subject ID, Dose Group, AE description, SOC, High-Level Group Term (HLGT), PT, duration of AE, reason reported as an SAE, severity, relationship to treatment, alternate etiology if not related, action taken with study treatment, whether the subject discontinued due to the AE, and AE outcome.

9.5. Pregnancies

Individual data listings of pregnancy reports will be provided if a pregnancy occurs post dosing:

- Maternal information will be presented in [Listing 24](#).
- Gravida and para information will be presented in [Listing 25](#).
- Live birth outcomes will be presented in [Listing 26](#), and still birth outcomes will be presented in [Listing 27](#).
- Spontaneous, elective, or therapeutic abortion outcomes will be presented in [Listing 28](#).

Birth control method(s) will be listed for each subject with a start and end date ([Listing 29](#)).

9.6. Clinical Laboratory Evaluations

Toxicity grading criteria for clinical laboratory results can be found in [Table 4](#). Unscheduled clinical laboratory evaluations will be included in listings of all clinical laboratory results, but excluded from tabular and graphical summaries by timepoint, except when calculating the maximum severity post baseline. Any pre-existing abnormal lab results at Screening and Baseline will be graded and presented in listings but will not be reported as an AE unless it is treatment-emergent (i.e. severity worsens after dosing). Clinical laboratory parameters that have grading criteria for both decreases (result lower than normal range) and increases (result higher than normal range) will be summarized separately by direction. Descriptions of each clinical laboratory summary are described below:

The following laboratory parameters will be presented (in order):

- CHEM: albumin, glucose, blood urea nitrogen, potassium, calcium, sodium, chloride, total protein, creatinine, triglycerides, total cholesterol, LDL cholesterol, HDL cholesterol, total carbon dioxide, creatine phosphokinase, phosphorus, magnesium, GGT, alkaline phosphatase, AST, ALT, total bilirubin, direct bilirubin, and serum cortisol.
- HEM: hemoglobin, hematocrit, lymphocytes, neutrophils, monocytes, eosinophils, basophils, platelet count, RBC, and WBC.
- COAG: prothrombin time, PTT, and international normalized ratio.

- UA: specific gravity by dipstick, pH by dipstick, occult blood by dipstick, leukocyte esterase by dipstick, RBC by complete UA, and WBC by complete UA (microscopic tests to be completed if dipstick urinalysis is abnormal). If microscopic results were obtained in the absence of an abnormal dipstick result (or without dipstick tests being done), results of the complete urinalysis or microscopy will still be summarized.

All safety laboratory results, severity, and change from baseline will be listed for each subject by Dose Group and timepoint. Abnormal laboratory results (laboratory results outside the normal range defined in the MOP) will be presented. Abnormal laboratory results that do not have toxicity grading ranges defined in the protocol will not have severity indicated in tables and listings of abnormal laboratory results, except as “ONR” (out of normal range).

- All CHEM results, including unscheduled visits, will be presented in [Listing 12](#). Abnormal results will be presented in [Table 23](#).
- All HEM results, including unscheduled visits, will be presented in [Listing 13](#). Abnormal results will be presented in [Table 24](#).
- All COAG results, including unscheduled visits, will be presented in [Listing 14](#), Abnormal results will be presented in [Table 25](#).
- All UA results, including unscheduled visits, will be presented in [Listing 15](#). Abnormal results will be presented in [Table 26](#).

All Screening results will be listed for each subject by Dose Group and visit:

- Serology results ([Listing 16](#)).
- Urine toxicology and alcohol urine results ([Listing 17](#)).
- Serum human chorionic gonadotropin (hCG) and pregnancy testing results ([Listing 18](#)).

Laboratory results will be summarized in tables and figures:

- Proportion of subjects with abnormal laboratory results by parameter, Dose Group, and timepoint for CHEM ([Table 27](#)), HEM ([Table 30](#)), COAG ([Table 33](#)), and UA ([Table 36](#)).
- Proportion of subjects with mild, moderate, or severe laboratory results by parameter, Dose Group, and timepoint for CHEM ([Table 28](#)), HEM ([Table 31](#)), COAG ([Table 34](#)), and UA ([Table 37](#)).
- Summary statistics of change from baseline by parameter, Dose Group, and timepoint for CHEM ([Table 29](#)), HEM ([Table 32](#)), COAG ([Table 35](#)), and UA ([Table 38](#)). UA character results (i.e. “1+”) will be excluded from change from baseline summaries.
- Graphical presentation of change from baseline at scheduled visits by Dose Group, and timepoint for each parameter as a series of box plots.
 - CHEM parameters will be presented beginning at [Figure 5](#) and continuing through [Figure 28](#).
 - HEM parameters will be presented beginning at [Figure 29](#) and continuing through [Figure 38](#).
 - COAG parameters will be presented for PTT ([Figure 39](#)), PT ([Figure 40](#)), and international normalized ratio ([Figure 41](#)).
 - UA parameters presented include specific gravity ([Figure 42](#)) and pH ([Figure 43](#)).

9.7. Vital Signs and Physical Evaluations

Toxicity grading criteria for VS results can be found in [Table 5](#). Unscheduled VS measurements will be listed, but excluded from tabular and graphical summaries by timepoint, except when calculating the maximum severity post baseline. If VS measurements are repeated due to technical errors, the initial measurements made in error will not be used for analysis but will be listed. Baseline is defined as the last VS measurement taken before dosing on Day 1.

VS parameters that have grading criteria for both decreases (result lower than normal range) and increases (result higher than normal range) will be summarized separately by direction.

The following VS parameters will be presented (in order): systolic blood pressure, diastolic blood pressure, pulse, respiratory rate, temperature.

VS results will be summarized in tables and figures:

- Proportion of subjects with mild, moderate, or severe VS results by parameter, Dose Group, and timepoint ([Table 39](#)).
- Summary statistics of change from baseline by parameter, Dose Group, and timepoint ([Table 40](#)).
- Graphical presentation of change from baseline by parameter, Dose Group, and timepoint (beginning at [Figure 44](#) and continuing through [Figure 58](#)).

All VS measurements, including height, weight, and BMI, will be presented in [Listing 19](#)

Abnormal physical exam findings will be presented in [Listing 20](#).

9.8. 12-Lead Standard Electrocardiogram

ECG measurements will be conducted in triplicate; the mean of triplicate values will be used for analysis, including change from baseline analysis. Toxicity grade criteria for 12-lead standard ECG parameters (mean of triplicate QTcF interval only) can be found in [Table 6](#). Unscheduled 12-lead standard ECG measurements will be listed but excluded from tabular and graphical summaries by timepoint, except when calculating maximum severity post baseline. Individual interval measurements and overall interpretations will be presented in [Listing 21](#) and [Listing 22](#), respectively. Other ECG findings will be presented in [Listing 23](#).

The following ECG parameters will be presented (in order): PR interval, QRS Duration, QT interval, QTcF interval, RR interval, and mean ventricular heart rate.

12-lead standard ECG results will be summarized in tables and figures:

- Summary of 12-lead standard ECG change in overall interpretation from baseline will be shown by Dose Group and timepoint ([Table 41](#)).
- Proportion of subjects with mild, moderate, or severe 12-lead standard ECG results will be presented for QTcF interval by Dose Group, timepoint, and severity ([Table 42](#)).
- Summary statistics of 12-lead standard ECG change from baseline results will be shown by parameter, Dose Group, and timepoint ([Table 43](#)). A categorical summary of QTcF by Dose Group and timepoint will be presented in ([Table 44](#)).
- Graphically, 12-lead standard ECG change from baseline results will be presented by parameter, Dose Group, and timepoint. PR interval will be presented in [Figure 59](#), QRS interval will be presented in [Figure 60](#), QT interval will be presented in [Figure 61](#), QTcF interval will be presented in [Figure 62](#),

RR interval will be presented in [Figure 63](#), and mean ventricular heart rate will be presented in [Figure 64](#).

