6. GENERAL STATISTICAL CONSIDERATIONS

6.1. General Principles

Summary statistics for continuous data will include the number of subjects included in analysis (N), mean, standard deviation (SD), median, minimum value (min), and maximum value (max). Summary statistics for discrete data will include frequencies and proportions and may include confidence intervals (CIs) for the proportion. When 95% CIs are given for a proportion, exact (Clopper-Pearson) CIs will be used, unless otherwise specified. All randomized subjects will be included in the summaries of subject demographics. The Safety Population will be used for summaries of safety endpoints and the PK Analysis Population or the PK Analysis Subset will be used for summaries of PK endpoints.

Denominators for safety endpoints will be the number of subjects in the Safety Population. Denominators for clinical laboratory, VS, and ECG results at planned study timepoints will be the number of subjects with available results at the specified timepoint for that parameter. Denominators for the conceptual “Maximum Severity Post Baseline” timepoint for clinical laboratory, VS, and ECG results will be the number of subjects with an observed result for the parameter obtained post dose.

The sort order for listings is indicated in the implementation note for each listing shell ([Appendix 3](#)). The sort order of clinical laboratory tests, VS, and ECG parameters is described in Section [9](#).

All safety and PK analyses will be performed by Dose Group as described in Section [3.3.2](#).

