9. SAFETY EVALUATION

All safety analyses will be performed using the Safety Population and will be presented by Dose Group. Placebo subjects enrolled in Cohort 3 that continued on to Cohort 6 will be counted separately for each dosing period, as detailed in Section [3.3.2](#).

Any medical condition that is present at the time that the subject is screened will be considered baseline and not reported as an AE, unless it worsens in severity or increases in frequency during the study. The denominators for proportion values will be indicated within the table or table header. AEs will be summarized for the number of subjects who experienced an AE and the number of events by Dose Group and Medical Dictionary for Regulatory Activities (MedDRA®) category. Toxicity grading scales for clinical adverse events are provided in All reported AEs will be included in the summaries and analyses.

Clinical laboratory, VS, and ECG results will also be used to assess safety. Results from these assessments will be graded by severity and presented in tables and figures by Dose Group for each post baseline timepoint. The analysis timepoints that will be summarized are presented in [Table 7](#). The most extreme severity grade observed after dosing will be summarized (Maximum Severity Post Baseline) and will include results from unscheduled visits. For tabular displays of clinical laboratory, VS, and ECG results by parameter, the maximum severity across all parameters within each category (CHEM, HEM, COAG, UA, VS, and ECG) will be included and summarized by timepoint (Any Parameter). CHEM, WBC (in COAG), and VS parameters will be displayed by event direction (increase or decrease).

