160 mg Fed	Baseline	x	x (x)	x (x)	x (x)
	...	x	x (x)	x (x)	x (x)
320 mg Fasted	Baseline	x	x (x)	x (x)	x (x)
	...	x	x (x)	x (x)	x (x)
640 mg Fasted	Baseline	x	x (x)	x (x)	x (x)
	...	x	x (x)	x (x)	x (x)
Placebo	Baseline	x	x (x)	x (x)	x (x)
	...	x	x (x)	x (x)	x (x)

Notes: The "Maximum Severity Post Baseline" row indicates the maximum severity of ECG results experienced across all subjects at any timepoint post baseline, including unscheduled assessments.

N=Number of subjects in the Safety Population with ECG results assessed at the respective timepoint.

Results from subjects in Cohort 3 that continued on to Cohort 6 are counted separately for each study part in both the Any Dose Group and the Placebo Dose Group.

Table 43: ECG Change from Baseline by Parameter, Severity, Dose Group, and Timepoint

[Implementation Note: Subjects who received VT-1598 in both Cohorts 3 and 6 will be included separately for each dosing period in the Any Dose Group. Similarly, subjects who received placebo in both Cohorts 3 and 6 will be included separately for each dosing period in the Placebo Dose Group.]

Parameter order: PR Interval, QRS Duration, QT Interval, QTcF Interval, RR Interval, Mean Ventricular Heart Rate.]

Dose Group	Timepoint	N	Change from Baseline			
			Mean	SD	Median	Min, Max
PR Interval (msec)						
Any Dose	Day 1, 4 h Post Dose	x	x	x	x	x, x
	Day 4	x	x	x	x	x, x
	Day 21	x	x	x	x	x, x
40 mg Fasted	Day 1, 4 h Post Dose	x	x	x	x	x, x
	...	x	x	x	x	x, x
80 mg Fasted	Day 1, 4 h Post Dose	x	x	x	x	x, x
	...	x	x	x	x	x, x
160 mg Fasted	Day 1, 4 h Post Dose	x	x	x	x	x, x
	...	x	x	x	x	x, x
160 mg Fed	Day 1, 4 h Post Dose	x	x	x	x	x, x
	...	x	x	x	x	x, x
320 mg Fasted	Day 1, 4 h Post Dose	x	x	x	x	x, x
	...	x	x	x	x	x, x
640 mg Fasted	Day 1, 4 h Post Dose	x	x	x	x	x, x
	...	x	x	x	x	x, x
Placebo	Day 1, 4 h Post Dose	x	x	x	x	x, x
	...	x	x	x	x	x, x
QRS Duration (msec)						
Any Dose	Day 1, 4 h Post Dose	x	x	x	x	x, x
...	...	x	x	x	x	x, x
...						

Notes: N=Number of subjects in the Safety Population with ECG measurements at the respective timepoint.

Results from subjects in Cohort 3 that continued on to Cohort 6 are counted separately for each study part in both the Any Dose Group and the Placebo Dose Group.

Table 44: Categorical Summary of QTcF by Dose Group and Timepoint

[Implementation Note: For all QTcF categories that specified gender, N based on gender should be used for calculating proportions]

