QTcF Category	Timepoint	N	Any Dose	40 mg Fasted	80 mg Fasted	160 mg Fasted	160 mg Fed	320 mg Fasted	640 mg Fasted	Placebo
			n (%)	n (%)	n (%)	n (%)	n (%)	n (%)	n (%)	n (%)
QTcF >450 ms, Male	Day 1, 4 h Post-Dose	x	x (xx)	x (xx)	x (xx)	x (xx)	x (xx)	x (xx)	x (xx)	x (xx)
		x	x (xx)	x (xx)	x (xx)	x (xx)	x (xx)	x (xx)	x (xx)	x (xx)
		x	x (xx)	x (xx)	x (xx)	x (xx)	x (xx)	x (xx)	x (xx)	x (xx)
	Day 7	x	x (xx)	x (xx)	x (xx)	x (xx)	x (xx)	x (xx)	x (xx)	x (xx)
		x	x (xx)	x (xx)	x (xx)	x (xx)	x (xx)	x (xx)	x (xx)	x (xx)
		x	x (xx)	x (xx)	x (xx)	x (xx)	x (xx)	x (xx)	x (xx)	x (xx)
	Day 21	x	x (xx)	x (xx)	x (xx)	x (xx)	x (xx)	x (xx)	x (xx)	x (xx)
		x	x (xx)	x (xx)	x (xx)	x (xx)	x (xx)	x (xx)	x (xx)	x (xx)
		x	x (xx)	x (xx)	x (xx)	x (xx)	x (xx)	x (xx)	x (xx)	x (xx)
QTcF >470 ms, Female	Day 1, 4 h Post-Dose	x	x (xx)	x (xx)	x (xx)	x (xx)	x (xx)	x (xx)	x (xx)	x (xx)
	...	x	x (xx)	x (xx)	x (xx)	x (xx)	x (xx)	x (xx)	x (xx)	x (xx)
QTcF >480 ms	Day 1, 4 h Post-Dose	x	x (xx)	x (xx)	x (xx)	x (xx)	x (xx)	x (xx)	x (xx)	x (xx)
	...	x	x (xx)	x (xx)	x (xx)	x (xx)	x (xx)	x (xx)	x (xx)	x (xx)
QTcF >500 ms	Day 1, 4 h Post-Dose	x	x (xx)	x (xx)	x (xx)	x (xx)	x (xx)	x (xx)	x (xx)	x (xx)
	...	x	x (xx)	x (xx)	x (xx)	x (xx)	x (xx)	x (xx)	x (xx)	x (xx)
30 ms ≤ QTcF increases from baseline < 60 ms	Day 1, 4 h Post-Dose	x	x (xx)	x (xx)	x (xx)	x (xx)	x (xx)	x (xx)	x (xx)	x (xx)
	...	x	x (xx)	x (xx)	x (xx)	x (xx)	x (xx)	x (xx)	x (xx)	x (xx)
QTcF increases from baseline ≥ 60 ms	Day 1, 4 h Post-Dose	x	x (xx)	x (xx)	x (xx)	x (xx)	x (xx)	x (xx)	x (xx)	x (xx)
	...	x	x (xx)	x (xx)	x (xx)	x (xx)	x (xx)	x (xx)	x (xx)	x (xx)

Note: N=Number of subjects in Safety Population with the ECG results assessed at the respective timepoint. N is calculated based on specified sex for “QTcF >450 ms, Male” and “QTcF >470 ms, Female” categories.

Table 45: VT-1598 Concentrations in Plasma by Dose Group – 0 h to 14 h Post Dose

Dose Group	Nominal Time ^a (h)										
	0	0.5	1.5	2	3	4	6	8	10	12	14
40 mg Fasted	x (x)	x (x)	x (x)	x (x)	x (x)	x (x)	x (x)	x (x)	x (x)	x (x)	x (x)
80 mg Fasted	x (x)	x (x)	x (x)	x (x)	x (x)	x (x)	x (x)	x (x)	x (x)	x (x)	x (x)
160 mg Fasted	x (x)	x (x)	x (x)	x (x)	x (x)	x (x)	x (x)	x (x)	x (x)	x (x)	x (x)
160 mg Fed	x (x)	x (x)	x (x)	x (x)	x (x)	x (x)	x (x)	x (x)	x (x)	x (x)	x (x)
320 mg Fasted	x (x)	x (x)	x (x)	x (x)	x (x)	x (x)	x (x)	x (x)	x (x)	x (x)	x (x)
640 mg Fasted	x (x)	x (x)	x (x)	x (x)	x (x)	x (x)	x (x)	x (x)	x (x)	x (x)	x (x)

Notes: Concentrations are reported in units of ng/mL.

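### Table 44, the only summary of QTcF >450 ms (men), >470 ms (women) and >480 ms, leaves out unscheduled ECGs and shows no post-baseline maximum row

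*SAP*

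**What the plan says.** SAP 9.8 sets the rule for unscheduled ECGs: "Unscheduled 12-lead standard ECG measurements will be listed but excluded from tabular and graphical summaries by timepoint, except when calculating maximum severity post baseline". The same section introduces the categorical table: "A categorical summary of QTcF by Dose Group and timepoint will be presented in" Table 44. The note under the Table 44 shell gives its denominator: "N=Number of subjects in Safety Population with the ECG results assessed at the respective timepoint". For the sex-specific categories the implementation note adds: "For all QTcF categories that specified gender, N based on gender should be used for calculating proportions".

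The exception for maximum severity is defined in SAP 9: "The most extreme severity grade observed after dosing will be summarized (Maximum Severity Post Baseline) and will include results from unscheduled visits". In the ECG displays it appears in Table 42, whose note says that the "row indicates the maximum severity of ECG results experienced across all subjects at any timepoint post baseline, including unscheduled assessments". Its denominator is set in SAP 6.1, where the number used at this conceptual "timepoint for clinical laboratory, VS, and ECG results will be the number of subjects with an observed result for the parameter obtained post dose".

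QTcF is graded in Protocol Appendix B and SAP Table 6. Grade 1 is a rise of more than 30 and up to 60 ms, Grade 2 is a rise above 60 ms with QTcF no higher than 500 ms, and Grade 3 is QTcF above 500 ms. Listing 21 is to show all ECG measurements, scheduled and unscheduled.

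**The concern.** The planned post-dose ECGs are at 4 hours, 72 hours (Day 4) and Day 21. Protocol 9.3 presumes Cmax at 6 hours, and no ECG is scheduled between 4 and 72 hours. An excursion in that interval would be recorded only if an extra ECG were taken, and the rule keeps extra ECGs out of Table 44. The table could then show zero in a category that a subject did reach.

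Separately, a reader usually wants the number of subjects who were ever above a threshold. Table 44 gives a count at each timepoint and does not say whether the same people recur.

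ECGs are part of the primary safety endpoint (SAP 3.2). Protocol 2.3.1 describes QT prolongation for ketoconazole and for voriconazole. What is at stake is the completeness of a summary table, not the data themselves.

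**Working it through.** The plan gives no figure on this point to reproduce. The check compares the rules and then works out what one subject would mean.

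**1. Does the exclusion reach Table 44?** Yes. SAP 9.8 describes the table as by Dose Group and timepoint, and its N is per timepoint. This rests on the text and not on the shell's row labels, several of which are blank.

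**2. Does another ECG summary cover these cuts?** Table 41 is overall interpretation, Table 42 is grade, and Table 43 and Figure 62 are change from baseline. Only Table 42 has a maximum row that includes unscheduled ECGs, and its grades have no cut at 450, 470 or 480 ms. Illustrative values on an unscheduled ECG:

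| Baseline to value (ms) | Rise (ms) | Table 42 grade | Absolute category met |
|---|---|---|---|
| Woman, 445 to 474 | 474 − 445 = 29 | none | >470 (female) |
| Man, 428 to 485 | 485 − 428 = 57 | Mild | >450 (male), >480 |
| Either sex, 380 to 445 | 445 − 380 = 65 | Moderate | none |
| Either sex, 400 to 485 | 485 − 400 = 85 | Moderate | >480, plus the sex-specific category |

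The first subject would be in neither table. The last two share a grade but not a category.

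**3. Which values are affected?** Assume that the Day 1 baseline is at or below the screening caps of 430 ms (men) and 450 ms (women).
- Ungraded but in a sex-specific category: a rise of at most 30 ms gives a ceiling of 430 + 30 = 460 ms in men and 450 + 30 = 480 ms in women. The ranges are >450 to 460 ms (men, baseline >420 to 430) and >470 to 480 ms (women, baseline >440 to 450).
- Above 480 ms: always graded under this assumption, but Mild reaches 430 + 60 = 490 ms in men and 500 ms in women, where Severe takes over.
- Above 500 ms: always Severe in Table 42.
- Change categories: Table 42 covers nearly all of them. Rises of exactly 30 or 60 ms fall on different sides of the two sets of cuts, and a Severe grade does not show the size of the rise.

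**4. Can such ECGs arise?** Protocol 6.7 allows a triplicate ECG at an unscheduled visit. Protocol 7.1.1 requires repeats every 30 minutes for waveform changes or possible cardiac symptoms; calling these unscheduled is an inference, since the SAP has no separate rule for them. Early withdrawal is run as an Unscheduled Visit under Protocol 5.2.1, but Protocol 6.6 gives it the Day 21 assessments, so its label is not settled.

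**5. What would one missed subject mean?** At planned sizes, in the >480 ms row:
- active Dose Group: 1/6 = 16.7%
- Placebo: 1/(2 × 6) = 1/12 = 8.3%
- Any Dose: 1/(6 × 6) = 1/36 = 2.8%

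In a sex-specific row the denominator is k, the number of that sex, which is not known in advance. For k = 1 to 6, 1/k is 100, 50, 33.3, 25, 20 and 16.7%. In Any Dose, if that sex makes up 12 to 24 of 36 (an assumption), it is 1/12 = 8.3% to 1/24 = 4.2%.

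**6. Distinct subjects.** For counts a, b and c at the three scheduled timepoints and N subjects, the distinct number on scheduled ECGs lies between max(a, b, c) and min(N, a + b + c).
- N = 6, counts 1, 1, 0: 1 or 2 subjects (16.7% or 33.3%).
- N = 6, counts 1, 1, 1: 1 to 3 subjects (16.7% to 50.0%).
- k = 3, counts 1, 1, 0: 1 or 2 subjects (33.3% or 66.7%).
- k = 1, counts 1, 1, 0: exactly 1 subject.

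With two or more non-zero counts, the bounds meet only when one timepoint already includes every subject.

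**The case against.** The strongest reply is that nothing is lost. Listing 21 holds every value, including triplicate means and change from baseline, and with six active subjects per group a reader can rebuild the counts by inspection. The dose-escalation halting rule (QTcF >500 ms or a rise >60 ms) does not use Table 44. A QTcF change recorded as an adverse event enters Tables 17 to 20, and Table 22 if it is non-serious and moderate or severe. The SAP applies the same exclusion to laboratory results and vital signs, and all primary analyses are descriptive. A maximum row also favours subjects with fewer ECGs. All of this stands and keeps the severity low. It does not close the gap, because neither the adverse event tables nor Table 42 show the 450, 470 and 480 ms cuts.

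The shell is also incomplete as it can be read. Table 7 lists a maximum-severity timepoint for ECG, and a row could sit behind a blank label. But SAP 9 ties that timepoint to severity grade, and no visible Table 44 row carries it.

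A reader might infer that anyone on the 30-minute prolongation repeats is already Moderate or Severe in Table 42. The documents do not support that. Repeats stop once the mean is within 60 ms of baseline, but neither Protocol 7.1.1 nor SAP 4.5 states what rise starts them.

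**Conclusion.** The point holds as a low-severity gap in summary reporting. Under SAP 9.8, a subject who passes 450 ms (men), 470 ms (women) or 480 ms only on an unscheduled ECG can be absent from the one table that reports those categories, and Table 42 does not supply the missing information. When two or more timepoints are non-zero, the number of distinct subjects is generally not determined, unless one timepoint already includes every subject.

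The percentages above show what one such subject would mean. They are not an expected error, because the documents give no basis for how often it would happen. The ungraded ranges assume that Day 1 baselines lie within the screening caps.

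Three stronger readings are tempting but not supported:
- That a QT signal could be hidden or escalation decisions affected: the values are listed, those above 500 ms are in Table 42, and the halting rules do not draw on Table 44.
- That distinct counts can never be recovered from several non-zero timepoints: the k = 1 case shows otherwise.
- That the protocol names QT prolongation as a risk of the whole azole class: Protocol 2.3.1 describes it for ketoconazole and voriconazole individually.

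**What to change.** Extend the SAP 9.8 exception to Table 44 and add a row, *Maximum Post Baseline (including unscheduled)*, to each category.

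- Count each subject once per dosing period, in line with SAP 3.3.2.
- Use the maximum triplicate-mean QTcF for the absolute categories and the maximum change for the change categories.
- Take as denominator the subjects with any post-dose ECG, as SAP 6.1 already does for maximum severity, and by sex where the category is sex-specific.
- Footnote the number of unscheduled ECGs per Dose Group, because subjects with more ECGs have more chances of a high maximum.

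The cost is one SAP sentence, one row per category and a footnote, all from data already collected. If the SAP is final, the row can be added and described in the clinical study report, as SAP 1 provides for deviations.
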